13.1.2 Primary Endpoint

The primary endpoint of this trial is the confirmed response rate using RECIST 1.1 criteria. All patients meeting the eligibility criteria who have signed a consent form and have begun treatment will be considered evaluable for the primary endpoint. A confirmed tumor response is defined to be a CR or PR noted as the objective status on 2 consecutive evaluations at least 4 weeks apart (within 8 weeks and not less than 4 weeks apart).

- For late responders to nivolumab (see section 5.7.1): Subjects who continue treatment beyond first progression (as determined by the initial investigator-assessed, RECIST 1.1-defined progression) will be considered to have investigator-assessed ‘progressive disease’ at the time of the initial progression event. However, if they subsequently experience a CR or PR, they may be designated as a ‘delayed responder’ for the purposes of determining ORR and thus, in the final analysis, be counted as a ‘responder’ for the study.

13.1.3 Statistical Design Overview

A patient that has a confirmed response is considered a treatment “success”. The following one-stage design with an interim analysis requires a maximum of 35 evaluable patients, and simultaneously discriminates between tumor response rates of 5% vs. 20%.

13.1.4 Final Analysis Decision Rule

Enroll 35 evaluable patients. If at least 4 patients have a confirmed tumor response (at least 11%) among the 35 evaluable patients, this agent would be considered worthy of further testing in this disease. If 3 or fewer patients have a confirmed tumor response, this agent will be considered negative and no further study would be warranted.

Interim Analysis Decision Rule: Enter 20 evaluable patients. If 2 or more of these 20 evaluable patients have a confirmed tumor response, the study will continue to full accrual. Otherwise, if fewer than 2 confirmed responses are observed, the study will be stopped early and the treatment will be considered ineffective in this patient population. Accrual will continue through the interim analysis phase, unless undue toxicity is observed.

13.1.5 Power and Significance Level

This design has 90% power to detect a true confirmed response rate of 20%, with a significance level of 0.09 if the true confirmed response rate is 5%. The likelihood of stopping at stage 1 of enrollment is 64.5% and 7% if the true confirmed response rate is 5% and 20%, respectively.

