Therefore, we have decided to use the data from two of our prior phase II studies of targeted agents, namely, pazopanib and cetuximab (the latter in combination with carboplatin) for calculating the sample size in this proposal because the cohort in these studies are similar to the current proposal. In the pazopanib study, patients had a median of 3 lines of therapy, and clinical benefit rate (CBR, PR + SD + CR) at 12 weeks was used to calculate the sample size. A CBR of 35% was estimated to be clinically meaningful, and the actual rate reported was > 50% [39]. The ORR was 6.1%, median TTP was 4.4 months (95% CI: 3.9–5.8 months) and the PFS-6 month was around 30-35% (read from the curve). In the cetuximab study [40], 70% of patients had 1 prior line of chemotherapy only. Although the ORR was 11.7% and the CBR rate was 60% (which is higher than the pazopanib study), the median TTP was quite short at 2.7 months, and the PFS-6 months was around 20-30% (read off the curve) [40]. Therefore, the average PFS at 24 weeks (6 months) is around 25-30% a benchmark for heavily-pretreated NPC patients, with a ORR between 6% to 20%.

These prior studies have shown that the response rate is generally around 5% in this disease setting [39-40]. If Nivolumab can increase the response rate to 20% or more, that would be exciting and worth further study. This protocol will assess the confirmed response rate as the primary endpoint. In addition this study will assess multiple secondary endpoints, including adverse events, tumor response to nivolumab based on immune-related response criteria (IRC), duration of response, progression-free survival (PFS), overall survival (OS), and laboratory correlates.

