14.1.2 Closed to Accrual

The study status is Permanently Closed to Accrual when no more patient enrollment slots are available and at least one patient is still actively receiving the study treatment. Sites are no longer permitted to enroll additional patients.

Patient slots are no longer available when the following criteria are met:

- The pre-specified number of evaluable patients has been successfully enrolled, treated, and evaluated.
- The study treatment has failed to meet the pre-specified efficacy goal at the stage 1 interim analysis.
- CTEP and the investigators agree that unacceptable toxicities preclude further enrollment.
- Investigators encounter any of the stopping criteria described in Section 5.3.

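### Section 13.1.5 understates the chance of early stopping at a true 5% response rate (73.6%, not 64.5%), and its significance level should read 0.08 rather than 0.09

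*Combined protocol and SAP*

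**What the plan says.** Section 13.1.3 sets up a design with a maximum of 35 evaluable patients to discriminate between confirmed response rates of 5% and 20%, with one interim analysis. Section 13.1.4 gives the decision rule:

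- Interim, at 20 evaluable patients: the trial goes on to 35 when the count of confirmed responses reaches two. The stopping side of the rule reads: "if fewer than 2 confirmed responses are observed, the study will be stopped early and the treatment will be considered ineffective".
- Final: "If at least 4 patients have a confirmed tumor response (at least 11%) among the 35 evaluable patients", the drug is considered worth further testing. With 3 or fewer it is considered negative.

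Section 14.1.2 treats the interim the same way. One of its criteria for permanently closing accrual is: "The study treatment has failed to meet the pre-specified efficacy goal at the stage 1 interim analysis".

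Section 13.1.5 then states four operating characteristics: power of 90% at a true 20%, a significance level of 0.09 at a true 5%, and the two early-stopping probabilities: "The likelihood of stopping at stage 1 of enrollment is 64.5% and 7% if the true confirmed response rate is 5% and 20%, respectively".

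**The concern.** The rule is fully specified, so all four figures in Section 13.1.5 are fixed by binomial arithmetic. The early-stopping figure at 5% looks too low. With 20 patients and a 5% response rate the expected number of responses is 1, and the trial stops at 0 or 1, so stopping should be well above 64.5%. The significance level also sits between what the rule gives with the interim stop and what it gives without it.

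These figures describe how the go/no-go rule behaves. The stopping probability at 5% shows how well the interim look screens out an inactive drug. They are likely to be carried into reports as the design properties of the trial, and a reader who checks them will find that they do not follow from the rule.

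**Working it through.** **Inputs.** Response rates 5% and 20%, and maximum N = 35 (13.1.3). Interim n = 20, stop at 1 or fewer; positive at 4 or more of 35 (13.1.4). Let X1 be the responses in the first 20 patients and X2 those in the next 15, independent binomials with the same rate p.

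**Formulas.**

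- P(stop) = (1 − p)^20 + 20 p (1 − p)^19
- P(positive) = P(X1 = 2) P(X2 ≥ 2) + P(X1 = 3) P(X2 ≥ 1) + P(X1 ≥ 4)

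**At a true 20%, where the stated figures reproduce.**

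- P(stop) = 0.0115 + 0.0576 = 0.0692 (unrounded terms summed). Stated: 7%.
- P(positive) = 0.1369 × 0.8329 + 0.2054 × 0.9648 + 0.5886 = 0.1140 + 0.1981 + 0.5886 = 0.9007. Stated: 90%.
- With the interim ignored, P(4 or more of 35) = 0.9395. So the stated 90% is the power with the stop enforced.

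**At a true 5%, where they do not.**

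- P(stop) = 0.95^20 + 20 × 0.05 × 0.95^19 = 0.3585 + 0.3774 = 0.7358. Stated: 64.5%. Gap: 73.6 − 64.5 = 9.1 points.
- P(positive) = 0.1887 × 0.1710 + 0.0596 × 0.5367 + 0.0159 = 0.0323 + 0.0320 + 0.0159 = 0.0801 (unrounded terms summed). Stated: 0.09.
- With the interim ignored, P(4 or more of 35) = 0.0958. The stated 0.09 is the two-decimal rounding of neither value.

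| | True rate | Stated | Exact, with stop | Exact, interim ignored |
|---|---|---|---|---|
| Early stopping | 5% | 64.5% | 73.6% | – |
| Early stopping | 20% | 7% | 6.9% | – |
| Significance level | 5% | 0.09 | 0.080 | 0.096 |
| Power | 20% | 90% | 90.1% | 93.9% |

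**Could another reading give 64.5%?**

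- Poisson approximation: 73.6%. Normal approximation: 69.6% with continuity correction, 50.0% without.
- Other interim sizes and cut-offs: the closest is 25 patients, stopping at 1 or fewer, which gives 64.2% at 5% but only 2.7% at 20%. It fails the stated 7%.
- Keeping 20 patients, 64.5% needs a true rate of about 6.2%, which is not the design's null.
- Using 40 patients at the final analysis does not touch the interim probability, and gives a significance level of 0.104 and power of 91.9%, further from the stated pair.

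**The case against.** The 64.5% has no good defence: no other section corrects it, and no alternative rule reproduces it together with the 7%.

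The case is better for 0.09. A stated significance level can be read as an upper bound, and 0.0801 lies below it, so the design controls error at the level claimed. The plan does not say how the figure was obtained. That stands as far as it goes: 0.09 overstates the error rate and misleads nobody in a harmful direction. But Section 13.1.5 gives it as the level of this design, next to a power figure that is right to rounding and includes the interim stop. On that basis the level is 0.08.

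It can also be said that none of this matters for the trial. The rule in Section 13.1.4 can be applied without Section 13.1.5, and no interim or final decision changes. That is true, and it limits the point to a correction of reported figures.

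**Conclusion.** The point holds. For the rule as written, early stopping at a true 5% is 73.6%, not 64.5%; this is the clear error. The significance level is 0.080 against a stated 0.09, a smaller discrepancy. Power and early stopping at 20% are correct as stated.

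Both errors are conservative. If the drug has a true rate of 5%, the trial stops early more often and gives a false positive less often than the plan claims. N, both boundaries, power and the risk of wrongly stopping an active drug are unchanged.

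The stopping figure assumes only that the 20 interim patients respond independently with the same probability. It does not depend on how many more patients are enrolled while the interim is awaited. The 0.080 assumes in addition that the same response probability applies to the later patients and that the interim stop is binding, as Sections 13.1.4 and 14.1.2 both say.

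**What to change.** In Section 13.1.5, replace 64.5% with 73.6% and 0.09 with 0.08 (exact value 0.0801). Leave 90% and 7% as they are. A short note that the figures are exact binomial values with the interim stop enforced would let a reader reproduce them.

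A separate, minor wording edit could go in the same amendment. Section 13.1.1 puts the response rate at about 5%, citing references 39 and 40, but reports 6.1% and 11.7% for those two studies. The sentence should be reconciled with those figures. The arithmetic above does not depend on it.

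The cost is wording only: two figures in 13.1.5 and one sentence in 13.1.1. The null rate, interim size, cut-offs, sample size and conduct stay as they are.

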13.1.6 Over Accrual

If more than the target number of patients are accrued, the additional patients will not be used to evaluate the stopping rule or used in any decision making process.

13.1.7 Other Considerations

Toxicity, quality/duration of response, and patterns of treatment failure observed in this study, as well as scientific discoveries or changes in standard care will be taken into account in any decision to terminate the study.

13.2 Sample Size/Accrual Rate

13.2.1 Sample Size

A total of 35 evaluable patients will be accrued per study design, unless the study is permanently closed at interim analysis or undue toxicity is observed. We anticipate accruing an additional 5 patients in order to account for ineligibility, cancellation, major treatment violation, or other reasons. Therefore, maximum accrual is 40 patients for this trial.

13.2.2 Accrual Time and Study Duration

We expect to accrue about 2 patients per month to this trial. Therefore, the accrual period for this Phase II study is expected to be about 20 months. The final analysis can begin approximately 26 months after the trial begins, i.e. as soon as the last patient has been observed for at least 6 months.

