4.4 Screening and General Guidelines

Following registration, patients should begin protocol treatment \leq 21 days. Issues that would cause treatment delays should be discussed with the Principal Investigator. If a patient does not receive protocol therapy following registration, the patient's registration on the study may be canceled. The Study Coordinator should be notified of cancellations as soon as possible. After the consent form is signed, refer to section 10 'Study Calendar' for screening procedures. Standard contrast CT will be done for assessing non-local recurrences. MRI will be used for assessing local recurrence. If dual PET and contrast CT is used to assess non-local recurrences at baseline, all subsequent radiological assessments must include a PET-CT.

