11.1 Schedule of Evaluations

For the purposes of this study, patients should be re-evaluated for objective tumor response at week 8 after the first dose of nivolumab, and then at week 16 and week 24, and then every 12 weeks thereafter. In addition to a baseline scan, confirmatory scans should also be obtained within 8 weeks (not less than 4) following initial documentation of objective response.

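### The 6-month minimum follow-up before the final analysis is shorter than the time needed to confirm a response first seen at the week-24 scan (low priority)

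*Combined protocol and SAP*

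**What the plan says.** - **Timing (13.2.2).** "The final analysis can begin approximately 26 months after the trial begins", that is, "as soon as the last patient has been observed for at least 6 months". The section does not say whether observation is counted from registration or from first dose.
- **Accrual (13.2.1, 13.2.2).** "We expect to accrue about 2 patients per month to this trial", and "maximum accrual is 40 patients for this trial": 35 evaluable plus 5 spare.
- **Scans (11.1).** Patients are "re-evaluated for objective tumor response at week 8 after the first dose of nivolumab, and then at week 16 and week 24", then every 12 weeks. In addition, "confirmatory scans should also be obtained within 8 weeks (not less than 4) following initial documentation of objective response".
- **Endpoint (13.1.2, 13.1.3).** A confirmed response is "a CR or PR noted as the objective status on 2 consecutive evaluations at least 4 weeks apart", with an upper limit of 8 weeks between the two. Only a confirmed response is a success. Every eligible, consented patient who has started treatment is evaluable, and there is no category for a response awaiting confirmation.
- **Decision rule (13.1.4).** Continue with at least 2 confirmed responses in 20; positive with at least 4 in 35.
- **Start of treatment (4.4).** "Following registration, patients should begin protocol treatment" within 21 days.

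**The concern.** Six months is just long enough to include the week-24 scan but not the scan that would confirm a response first seen there. The most recently enrolled patients would then have less opportunity than the others to become confirmed responders, and any error in the observed rate would be downward. The final rule turns on single patients: 4 responses in 35 is positive and 3 is negative.

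The plan also sets no data cut-off and does not say how a pending confirmation is scored. The analysis date is therefore open to choice while pending responses are visible. The protocol expects some responses to come late: Sections 5.7.1 and 13.1.2 allow delayed responders to count.

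**Working it through.** **1. The plan's own timeline.** 40 patients / 2 per month = 20 months; 20 + 6 = 26 months. The stated figure reproduces.

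**2. Weeks needed against weeks allowed.** Six months = 6 × 365.25 / 12 / 7 = 26.1 weeks.

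| First response at | Confirmed, from first dose | Confirmed, from registration with 21-day lag |
|---|---|---|
| Week 16 | weeks 20-24 | weeks 23-27 |
| Week 24 | weeks 28-32 | weeks 31-35 |

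For a week-24 response the shortfall is 28 − 26.1 = 1.9 to 32 − 26.1 = 5.9 weeks. With the full lag it is 4.9 to 8.9 weeks, and the week-24 scan itself falls at week 27 from registration.

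**3. Patients affected.** At 2 per month, patients enter about 2.17 weeks apart. On the earliest permitted date the last four have about 26.1, 28.3, 30.4 and 32.6 weeks, so three have less than 32 (5.9 weeks = 1.36 months; 1.36 × 2 = 2.7). With the full lag, 8.9 weeks = 2.05 months; 2.05 × 2 = 4.1, so about 4-5 patients. These patients entered 26 to 32 weeks before the analysis (26 to 35 with the lag).

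**4. Power under the stated rules.** Let X1 be the responses in the first 20 patients and X2 those in the last 15.

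Power = Σ (x = 2 to 20) P(X1 = x) · P(X2 ≥ 4 − x)

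At a response rate of 0.20 this gives 0.9007, which reproduces the 90% in 13.1.5.

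**5. Effect of the early date.** Give the last k patients response probability 0.20(1 − f), where f is the share of responders whose first response is at week 24. The documents give no value for f, so a range is shown.

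| f (assumed) | Power, k = 3 | Power, k = 5 |
|---|---|---|
| 10% | 0.8989 | 0.8976 |
| 20% | 0.8970 | 0.8942 |
| 30% | 0.8950 | 0.8906 |
| 100% (extreme) | 0.8791 | 0.8573 |

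- Expected responses missed, 0.20 · f · k: from 0.20 × 0.10 × 3 = 0.06 to 0.20 × 0.30 × 5 = 0.30.
- Chance of missing at least one, 1 − (1 − 0.20f)^k: 1 − 0.98³ = 6% (k = 3, f = 10%); 1 − 0.96³ = 12% (k = 3, f = 20%); 1 − 0.94⁵ = 27% (k = 5, f = 30%).
- Type I error at a rate of 0.05 only falls: from 0.0801 to between 0.0787 (k = 3, f = 10%) and 0.0729 (k = 5, f = 30%). These are computed from the stated rules; 13.1.5 states 0.09, a separate matter that does not affect this point.

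**6. How often one response decides.** At a rate of 0.20, the chance of passing the interim and ending on exactly 4 responses is P(total = 4) − P(X1 = 0)P(X2 = 4) − P(X1 = 1)P(X2 = 3) = 0.0830 − 0.0115 × 0.1876 − 0.0576 × 0.2501 = 0.066. In those trials one missed response would reverse the conclusion.

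**The case against.** **The date is a floor.** Section 13.2.2 is a planning projection with permissive wording. Follow-up runs for up to 3 years (5.4), and 11.1 calls for the confirmatory scan whatever the analysis date. A reader might infer that the plan scores late responders as failures. It does not say so: it neither states how a pending confirmation is classified nor forbids waiting. This stands. What can be said is conditional: on the earliest permitted date, such a patient is evaluable and is not yet a success.

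**Spare slots may remove the problem.** Under 13.1.6, patients beyond the target play no part in the decision. If all 40 enrol and all are evaluable, the 35th enters at month 17.5 and has 8.5 months (about 37 weeks) by month 26, enough even with the full lag. If two spare slots are used up, the 35th evaluable patient enters at month 18.5 and has 7.5 months (about 32.6 weeks), enough without the lag. This also stands. On the 26-month timeline without the lag, the gap appears only when most spare slots are used. If accrual instead stops at 35 evaluable patients, the 6-month floor applies to the last of them directly.

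**Any finite cut-off misses something.** Scans continue every 12 weeks, so a response first seen at week 36 in a late entrant would be missed at week 32 too. That is true, and week 24 plus 8 is a convention. The reason to choose it is that the plan's 6 months already includes the week-24 scan when counted from first dose; reading that scan without its confirmation is the inconsistency.

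**The lag is a worst case.** Twenty-one days is a maximum, and it matters only if observation is counted from registration. The figures for 4-5 patients and weeks 31-35 depend on both.

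**Conclusion.** The mismatch is real and follows from the protocol's own figures: analysis is permitted from about week 26, whereas confirmation of a week-24 response comes at weeks 28-32. It concerns roughly the last 3 evaluable patients, about 4-5 with the full lag, and fewer if spare slots go unused.

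A reader might also infer a material loss of power. The numbers do not support that: with f between 10% and 30%, power goes from 0.901 to between 0.899 and 0.891, and type I error does not rise. These results assume analysis on the earliest permitted date, entry at 2 per month, and a share f that the documents do not supply.

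The point is low priority. It is worth making because the bias runs one way, the threshold is 4 of 35, and the repair is cheap.

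**What to change.** In 13.2.2, state that the final analysis begins when every evaluable patient counted in the decision rule has had the week-24 scan, and any response first documented by that scan has either had its confirmatory scan or passed the 8-week window. On the nominal schedule this is at most 32 weeks from the last such patient's first dose; the ±7-day imaging tolerance in Section 10 could add a week.

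Allow earlier closure only for patients who have died, who are already confirmed responders, or who have progressed and are not being treated beyond progression. Patients treated beyond progression must stay open because 13.1.2 can still count them as responders.

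Restate the timeline as about 27.5-28 months: 20 + 32 weeks (7.4 months) = 27.4, or 20 + 35 weeks (8.1 months) = 28.1 with the full lag.

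The cost is a delay of about 6 weeks, or up to 9 weeks if timed from registration. No visits are added, because the scans are already in the schedule.

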13.3 Stratification Factors and Subset Analyses for Primary Endpoint

Since the study is not randomized, there are no stratification factors for randomization purposes. In an exploratory analyses, response rates will also be summarized in the following subsets: PD-L1, PD-L2, PD-1 and PD-1 IHC expression levels (positive vs. negative expression), number of lines of prior chemotherapy for metastatic or recurrent NPC (1 or > 1 line), and prior exposure to EBV vaccines.

13.4 Analysis of Secondary Endpoints

This study will assess multiple secondary endpoints, including adverse events, tumor response to nivolumab based on immune-related response criteria (IRC), duration of response, progression-free survival (PFS), overall survival (OS), and laboratory correlates. The analysis population for these endpoints will be the same as that for the primary endpoint – i.e., all patients meeting the eligibility criteria who have signed a consent form and have begun treatment.

13.4.1 Adverse Events

All patients that have initiated treatment will be considered evaluable for assessing adverse events. The maximum grade for each type of adverse event will be recorded for each patient, and frequency tables will be reviewed to determine adverse event patterns. Only the severe or worse adverse events will be assessed, regardless of relationship to the study treatment. In addition, the following adverse events will be captured and followed over time: pneumonitis, endocrinopathy, infusion-related reactions, diarrhea, skin events [23].

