1.2 Secondary Objectives

1.2.1 Tumor response to nivolumab based on immune-related response criteria (IRC).

1.2.2 Duration of response.

1.2.3 Progression-free survival and overall survival.

1.2.4 Safety and tolerability.

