5.6.3 For Grade 3 or Grade 4 Symptoms

(Severe reaction), Grade 3 symptoms: prolonged [i.e., not rapidly responsive to symptomatic medication and/or brief interruption of infusion]; recurrence of symptoms following initial improvement; hospitalization indicated for other clinical sequelae [e.g., renal impairment, pulmonary infiltrates]). Grade 4 symptoms: (life threatening; pressor or ventilator support indicated).

Immediately discontinue infusion of nivolumab. Begin an IV infusion of normal saline, and treat the subject as follows. Recommend bronchodilators, epinephrine 0.2 to 1 mg of a 1:1,000 solution for subcutaneous administration or 0.1 to 0.25 mg of a 1:10,000 solution injected slowly for IV administration, and/or diphenhydramine 50 mg IV with methylprednisolone 100 mg IV (or equivalent), as needed. Patient should be monitored until the investigator is comfortable that the symptoms will not recur. Nivolumab will be permanently discontinued. Investigators should follow their institutional guidelines for the treatment of anaphylaxis. Remain at bedside and monitor patient until recovery from symptoms. In the case of late-occurring hypersensitivity symptoms (e.g., appearance of a

localized or generalized pruritis within 1 week after treatment), symptomatic treatment may be given (e.g., oral antihistamine, or corticosteroids).

- Please note that late occurring events including isolated fever and fatigue may represent the presentation of systemic inflammation. Please evaluate accordingly.

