6.2 Guideline for Specific Nivolumab Related Adverse Events

Skin Rash and Oral Lesions	Management/Next Dose for Nivolumab
≤ Grade 1	No change in dose *
Grade 2	Hold* until ≤ 1 Grade resolved. Consider steroid treatment if > 7 days. Resume at same dose level.
Grade 3	Hold* until ≤ Grade 1. Consider steroid treatment. Resume at same level at investigator discretion
Grade 4	Off protocol therapy
*Patients with purpuric or bullous lesions must be evaluated for vasculitis, Steven-Johnson syndrome, TEN, and autoimmune bullous disease including oral lesions of bullous pemphigus/pemphigoid. Pruritus may occur with or without skin rash and should be treated symptomatically if there is no associated liver or GI toxicity. Note skin rash typically occurs early and may be followed by additional events particularly during steroids tapering.	
Recommended management: AE management guidelines	

Liver Function: ALT, AST, total bilirubin	Management/Next Dose for Nivolumab
≤ Grade 1	Continue nivolumab and monitor liver enzymes as per protocol.
Grade 2	Hold until ULN or baseline. Resume at same dose level. Consider steroid treatment > 7 days
Grade 3	Off protocol therapy
Grade 4	Off protocol therapy
Continuation of nivolumab during active immune-mediated hepatitis may exacerbate the inflammation. Holding drug to evaluate LFT changes and early treatment are recommended. LFT changes may occur during steroid tapers from other events and may occur together with other GI events including cholecystitis /pancreatitis.	
Recommended management: see Hepatic AE management algorithm (Appendix C)	

Diarrhea/ Colitis	Management/Next Dose for Nivolumab
≤ Grade 1	Hold until Grade 0 or baseline. No change in dose
Grade 2	Hold until Grade 0 or baseline. Consider steroid treatment if lasting > 7 days, if condition does not improve within a reasonable time frame, the patient should be withdrawn from study if this is in the best interest of the patient as judged by the investigator.
Grade 3	Off protocol therapy.
Grade 4	Off protocol therapy

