Distinguishing inflammatory pneumonitis is often a diagnosis of exclusion for patients who do not respond to antibiotics and have no causal organism identified including influenza. Most patients with respiratory failure or hypoxia will be treated with steroids. Bronchoscopy may be required and analysis of lavage fluid for lymphocytic predominance may be helpful. Patients with new lung nodules should be evaluated for sarcoid like granuloma. Please consider recommending seasonal influenza killed vaccine for all patients.	
Recommended management: See Pulmonary Adverse Event Management Algorithm (Appendix C)	

Other GI, Nausea-Vomiting	Management/Next Dose for Nivolumab
≤ Grade 1	No change in dose.
Grade 2	Hold until ≤ Grade 1. Resume at same dose level after resolution to ≤ Grade 1. If recurs after resuming nivolumab, evaluate for gastritis duodenitis and other immune adverse events or other causes
Grade 3	Hold pending evaluation until ≤ Grade 1. Evaluate for gastritis duodenitis and other immune adverse events or other causes. Resume at same dose level. If symptoms do not resolve within 7 days with symptomatic treatment patients should go off protocol therapy
Grade 4	Off protocol therapy
Patients with grade 3 (or recurrent grade 2) nausea-vomiting should be evaluated for upper GI inflammation and other immune related events.	

Fatigue	Management/Next Dose for Nivolumab
≤ Grade 1	No change in dose.
Grade 2	No change in dose
Grade 3	Hold until ≤ Grade 2. Resume at same dose level
Grade 4	Off protocol therapy
Fatigue is the most common adverse event associated with immune checkpoint therapy. Grade 2 or greater fatigue should be evaluated for associated or underlying organ involvement including pituitary, thyroid, and hepatic, or muscle (CPK) inflammation	

Neurologic events	Management/Next Dose for Nivolumab
≤ Grade 1	Hold dose pending evaluation and observation. Resume with no change in dose.*
Grade 2	Hold dose pending evaluation and observation. Hold until ≤ Grade 1.* Off protocol therapy if treatment with steroids is required. Resume at same dose level for peripheral isolated n. VII (Bell's palsy).
Grade 3	Off protocol therapy
Grade 4	Off protocol therapy
*Patients with any CNS events including aseptic meningitis, encephalitis, symptomatic hypophysitis, or myopathy, peripheral demyelinating neuropathy, cranial neuropathy (other than peripheral n. VII), Guillain Barre syndrome, myasthenia gravis should be off study.	

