7.4 Routine Adverse Event Reporting

All Adverse Events **must** be reported in routine study data submissions. **AEs reported expeditiously through CTEP-AERS must also be reported in routine study data submissions.**

Adverse event data collection and reporting, which are required as part of every clinical trial, are done to ensure the safety of patients enrolled in the studies as well as those who will enroll in future studies using similar agents. AEs are reported in a routine manner at scheduled times during the trial using Medidata Rave.

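### Section 13.4.1 contradicts itself on whether adverse events below severe are summarised; if its severe-only sentence governs, some lower-grade events that interrupt or end nivolumab drop out of the tolerability result

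*Combined protocol and SAP*

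**What the plan says.** Section 1.2 lists "1.2.4 Safety and tolerability" as a secondary objective. Its analysis is in section 13.4.1, which counts every patient who has started treatment and then makes three statements in sequence:

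- "The maximum grade for each type of adverse event will be recorded for each patient", with frequency tables reviewed for patterns.
- "Only the severe or worse adverse events will be assessed, regardless of relationship to the study treatment".
- A further list of five types, for which no grade floor is given: "the following adverse events will be captured and followed over time: pneumonitis, endocrinopathy, infusion-related reactions, diarrhea, skin events [23" (the open bracket begins a reference number).

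Section 7.4 requires that all adverse events "be reported in routine study data submissions", so lower-grade events are collected. Section 13 plans no summary of dose delays or of discontinuations due to adverse events.

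**The concern.** The first statement points to tables over all grades. The second, with the word only, points to severe events alone. The third adds five types, which would add little if all grades were assessed anyway. An analyst could follow either instruction and claim to have followed the plan.

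The choice matters because the protocol's own action thresholds lie below severe. Sections 6.2 and 5.3 interrupt, and in places end, nivolumab for grade 1 or grade 2 events, and several of the organ systems concerned are not among the five. A summary cut at severe could therefore omit events for which a patient's treatment was held or stopped. That is a weak basis for a statement on tolerability.

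**Working it through.** No figure in the plan needs reproducing here. The check sets section 13.4.1 beside the action rules.

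**Step 1: what severe means.** Section 13.4.1 gives no grade number. Section 5.6.3, on grade 3 or 4 infusion reactions, reads "Severe reaction), Grade 3 symptoms: prolonged". That supports severe as grade 3, but it remains an inference.

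**Step 2: the eleven event tables in section 6.2 against the five types.**

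| Table in 6.2 | Among the five | Grade 1 or lower | Grade 2 |
|---|---|---|---|
| Skin and oral | yes | no change | hold |
| Liver | no | continue | hold |
| Diarrhea/colitis | yes | hold | hold |
| Pancreas | no | hold | hold |
| Pneumonitis | yes | hold | hold; off study if steroids needed |
| Other GI, nausea/vomiting | no | no change | hold |
| Fatigue | no | no change | no change |
| Neurologic | no | hold | hold; off therapy if steroids needed |
| Endocrine | yes | hold | hold |
| Fever | no | hold | hold |
| Cardiac | no | hold | hold if myocarditis suspected; off therapy if confirmed |

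Infusion reactions, the fifth listed type, are handled in section 5.6. The liver entry at grade 2 reads "Hold until ULN or baseline. Resume at same dose level. Consider steroid treatment > 7 days". The neurologic entry at grade 2 includes "Off protocol therapy if treatment with steroids is required". The cardiac rows apply to grade 2 or higher.

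**Step 3: count.** 11 tables − 4 covered = 7 not covered. Of these 7, all but fatigue hold at grade 2: 7 − 1 = 6. Four also hold at grade 1 or lower: pancreas, neurologic, fever, cardiac.

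**Step 4: rules outside 6.2.** Section 5.3(c) ends treatment for certain grade 2 uveitis, eye pain or blurred vision; eye events are not among the five. Section 5.3(d) normally ends treatment after more than two delays for the same type of event at grade 2 or above.

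**Step 5: what to take back out.** Section 5.5.2 deems symptomatic hypophysitis, and CNS events such as aseptic meningitis or encephalitis, to be grade 3. These fall inside the severe set whatever their nominal grade.

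**Step 6: size in patients.** The risk list in section 7.1 (n = 2069) gives frequency bands by term, not by grade. Myocarditis is in the band below 3%, at most 0.03 × 40 = 1.2 patients at maximum accrual. Liver enzymes, lipase, amylase, pancreatitis and uveitis are each in the band up to 20%, at most 0.20 × 40 = 8 patients per term. These are ceilings over all grades and cannot be added into a rate of lower-grade, treatment-holding events.

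To fix the scale only, let p be an assumed share of patients whose worst event in an uncovered type was a lower-grade one that held or ended treatment. The number missing for that type is p × n:

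| p (assumed) | n = 35 | n = 40 |
|---|---|---|
| 5% | 1.75 | 2 |
| 10% | 3.5 | 4 |
| 20% | 7 | 8 |
| 30% | 10.5 | 12 |

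Nothing in the documents supports choosing one row over another.

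**The case against.** The best defence is the maximum-grade sentence. It can be read as promising tables over all grades, with the severe-only sentence limiting just the narrative assessment. On that reading nothing is lost. It is a fair reading, and it is why a reader who infers that tolerability will certainly look better than it was goes further than the text allows. But it does not remove the problem: the word only and the separate list of five point the other way, and the section does not say which governs.

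Four further points limit the concern:

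- A reader might infer that all grade 1-2 liver events hold treatment. Section 6.2 continues nivolumab at grade 1 or lower; only grade 2 liver events are held.
- The gravest examples are not invisible. Confirmed myocarditis of grade 2 or higher calls for admission under 6.2, and under section 7.3.3 a grade 2 event with at least 24 hours in hospital needs an expedited report. That stands, but an expedited report is not the planned safety summary.
- The stopping rule in 13.5.2 uses grade 4 and grade 5 events, so early protection of patients does not depend on this restriction. There is also no safety hypothesis test to distort.
- All events are collected, so all-grade tables can be made at any time. This lowers the cost of the defect and of its repair, but it does not make the plan clear.

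**Conclusion.** The point holds in conditional form. Section 13.4.1 is internally inconsistent. If the severe-only sentence is followed, the summary leaves out events that the protocol treats as reason to interrupt or end nivolumab: liver at grade 2; pancreatic, neurologic and cardiac at grades 1-2, apart from CNS events deemed grade 3; fever at grades 1-2; nausea/vomiting at grade 2; and some grade 2 uveitis. The result may then understate the burden that objective 1.2.4 is meant to describe.

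This rests on two assumptions: that severe means grade 3 or higher, and that the severe-only sentence overrides the one before it. The extent is clear in structure (six of seven uncovered tables hold at grade 2) but not in patients. A reader might want to attach a patient count, but any such figure would rest on an assumed rate. This is a cheap improvement to the safety analysis. It does not affect the primary endpoint, the sample size or safety monitoring.

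**What to change.** Replace the severe-only sentence in section 13.4.1 with: *All adverse events will be tabulated by term and maximum grade (all grades, and grade 3 or worse), regardless of attribution and for events at least possibly related.* Stating the grade number also settles what severe means.

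Add: *The number of patients with a dose delay or permanent discontinuation due to an adverse event will be reported by type and grade, where the case report form records the reason.* The condition is needed because the documents do not show that the form links a delay to its causal event.

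Extending the list of five followed types is optional once all-grade tables exist. The cost is a few more tables and possibly a less favourable-looking profile. The event data are already required under section 7.4, and no clinical rule changes.
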